6.1.2.4 Image interpretation

MR images will be interpreted by a single radiologist. The following criteria for tumor identification are widely accepted in the literature and are used in routine clinical practice: round or ill-defined, low-signal-intensity focus in the peripheral zone; or homogeneous signal mass with indistinct margins in the transition zone on T2-weighted imaging; high signal intensity on DWI and low ADC values when compared to the remainder of the prostate tissue.¹⁸ In addition, dynamic contrast-enhanced images will be analyzed using a FDA-approved software for

pharmacokinetic evaluation (VividLook with Versavue Enterprise, iCAD, Nashua, NH). Suspicious areas for tumor are defined as those with increased relative peak enhancement and subsequent decrease in signal intensity—"rapid wash-in and wash-out pattern"). Color-coded map will be generated to highlight areas with high microvascular permeability and low to medium extracellular volume fraction.¹⁹

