6.1.2.5 MRI-US image fusion

Anatomic co-registration of biopsy samples and MRI findings are essential in this proposal. Transrectal ultrasound images will be fused with initial MRI performed prior to therapy using a specialized device (UroStation; Koelis, Grenoble, France). This technology allows 3-dimensional anatomic co-registration of volumetric transrectal ultrasound (TRUS) and MRI acquisitions. Once the TRUS and MRI volumes are co-registered, the urologist can use the real-time fusion dataset to perform routine sextant biopsies and also target biopsies directly to the suspicious areas on MRI. Furthermore, this system allows for saving a 3D map of the prostate with the biopsy tracts of the needle biopsies and data from pathologic analysis, once it becomes available, can be loaded into the system for further analysis. Because these 3D maps can be loaded into the biopsy US unit prior to performing the follow-up biopsy after treatment, we will use this capability to facilitate the anatomic coregistration of the initial pre-treatment biopsies and the repeat biopsy performed after treatment.²⁰

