6.1.2.6 Evaluation of changes in tumor volume and tumor activity

Tumor volume will be assessed using a planimetric approach.²¹ On each MRI prostate section the outline of suspicious areas will be traced on the computer screen and the surface area will be calculated. After counting the number of separate foci and defining the most representative site of origin, tumor foci volume will be calculated by multiplying the sum of the suspicious surface areas by the slice thickness (usually 2-3 mm).

Tumor activity will be assessed using apparent diffusion coefficient (ADC) derived from diffusion-weighted imaging, which has been shown to correlate with Gleason score and percentage of tumor on core biopsy (as surrogates for tumor aggressiveness).^{22,23} ADC values will be derived by drawing a region of interest on the confirmed tumors, and expressed as mean values and histograms.

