7.6 Unblinding Procedures

This is an open-label study. Unblinding procedures will not be applicable.

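### The plan does not require the single MRI reader to be masked to time point, and it leaves open which lesions count for ADC at 2 months

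*Combined protocol and SAP*

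**What the plan says.** All of the following is in the combined protocol and SAP.

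- **Reader.** Section 6.1.2.4: "MR images will be interpreted by a single radiologist". No second or repeat reading is planned.
- **Masking.** Section 7.6: "This is an open-label study. Unblinding procedures will not be applicable". No section says whether the reader sees scan dates, time points or clinical data, or in what order the scans are read.
- **Volume.** Section 6.1.2.6: "On each MRI prostate section the outline of suspicious areas will be traced on the computer screen and the surface area will be calculated". The summed area is multiplied by slice thickness.
- **Activity.** Section 6.1.2.6: "ADC values will be derived by drawing a region of interest on the confirmed tumors, and expressed as mean values and histograms". The term *confirmed* is not defined, either by method (biopsy or imaging) or by time (baseline or each scan).
- **Lesion criteria.** Section 6.1.2.4 lists T2 appearance, including foci and masses without sharp borders, together with "high signal intensity on DWI and low ADC values when compared to the remainder of the prostate tissue".
- **Co-registration.** Section 6.1.2.5 fuses ultrasound with the pre-therapy MRI and keeps the 3D maps to "facilitate the anatomic coregistration of the initial pre-treatment biopsies and the repeat biopsy performed after treatment". Section 4.4.2.2 describes the same ultrasound–MRI fusion and tracking of biopsy sites.
- **Use of the data.** Section 10.3 reports the MRI changes per patient and as mean change with standard deviation. No test, threshold or power is given.

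**The concern.** There are two separate weaknesses.

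First, the measurement is a judgement. Lesion edges are placed by hand on lesions that the protocol itself describes as poorly demarcated. Section 1.5 states that a measurable MRI response is expected, and every second scan comes after treatment. With no control arm, any tendency to draw smaller outlines on scans known to be post-treatment goes directly into the within-patient change.

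Second, the set of lesions with an ADC value at 2 months may depend on the ADC itself. If tumors are identified afresh at follow-up, a lesion whose ADC has risen to that of the surrounding tissue no longer meets one of the criteria. It may then receive no region and no value, and the lesions that remain would be those that responded less.

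Multiparametric MRI is the only measure named for objective 2.1.6 (preliminary anti-tumor activity). Section 2.2 does not list that objective among those it calls exploratory, and Section 6.1 sets RECIST aside. Section 1.4 says the results are meant to prepare for randomized trials. Enrolling more patients would not remove a systematic reading error.

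**Working it through.** The plan gives no effect size, standard deviation or power for the MRI endpoint, so it has no figure to reproduce. The calculations below are illustrations under stated assumptions.

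**1. Sensitivity of hand-traced volume to edge placement.** Assume a spherical lesion of diameter d, traced a distance s too far inward all round. The fraction of volume lost is 1 − ((d − 2s)/d)³.

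| d | s = 0.5 mm | s = 1 mm |
|---|---|---|
| 10 mm | 1 − 0.9³ = 27% | 1 − 0.8³ = 49% |
| 15 mm | 1 − (14/15)³ = 19% | 1 − (13/15)³ = 35% |
| 20 mm | 1 − 0.95³ = 14% | 1 − 0.9³ = 27% |

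**2. Constant habit against a shift at follow-up only.** Suppose a lesion truly shrinks from 20 to 15 mm in diameter.

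- True reduction: 1 − (15/20)³ = 57.8%.
- Both scans traced 0.5 mm inward: 1 − (14/19)³ = 60.0%, an error of 2.2 percentage points.
- Only the follow-up scan traced 0.5 mm inward: 1 − (14/20)³ = 65.7%, an error of 7.9 points.

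A steady tracing habit largely cancels. A habit that changes with knowledge of the time point does not.

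**3. Chance that the ADC gap arises.** Assume each patient has probability p of no visible lesion at 2 months. The chance of at least one such patient is 1 − (1 − p)ⁿ. The plan gives both 7 subjects (Study Summary; accrual sentence in Section 10.2) and ten (Section 10.2), so both are shown.

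- n = 7: 30% at p = 0.05, 92% at p = 0.30.
- n = 10: 40% at p = 0.05, 97% at p = 0.30.

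**4. Effect on mean ADC change if the best responders have no value.** Assume normally distributed changes, in units of their between-patient SD, and remove the k largest from each sample (400,000 simulated samples).

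- n = 7: the mean moves toward no effect by 0.22 SD (k = 1) or 0.42 SD (k = 2). With k = 1, the average observed SD falls from 0.96 to 0.80.
- n = 10: the mean moves by 0.17 SD (k = 1) or 0.32 SD (k = 2). With k = 1, the average observed SD falls from 0.97 to 0.84.

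For scale, the 95% confidence half-width of a mean, t(0.975, n − 1)/√n, is 0.92 SD at n = 7 and 0.72 SD at n = 10.

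**5. What the co-registration covers.** Sections 4.4.2.2 and 6.1.2.5 link ultrasound to the initial MRI and one biopsy session to the next. Neither describes matching the baseline MRI to the follow-up MRI, or placing an ADC region on the second scan.

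**The case against.** The strongest reply is that the plan is silent here rather than wrong, and that little depends on it.

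- *A reader might infer that the scans are read unmasked.* The documents do not say so. Section 7.6 concerns treatment assignment. What stands is that masking to time point is not required, so the plan gives no protection.
- *A reader might infer that the endpoint loses its best responders.* That follows only if confirmation is judged again at 2 months. Section 6.1.2.5 allows pathology results to be loaded into the map, so confirmation at baseline is a natural reading. If the same site is then measured again, nobody is lost. What stands is that the plan does not choose between the readings.
- *The gap does not extend to volume.* Under Section 6.1.2.6, if no suspicious area is traced, the summed area, and so the volume, is 0.
- *One reader is not a defect in itself.* Step 2 shows that a constant habit mostly cancels when the same person reads both scans.
- *The edge shifts are assumed.* They show how sensitive the method is, not how large any bias is.
- *The two biases oppose each other for ADC.* Expectation could enlarge the change, while loss of normalised lesions would reduce it. This leaves the net direction unknown; it does not show that they cancel. Volume is exposed only to the first.
- *The consequence is limited.* No decision rests on the endpoint, and the stopping rules in Sections 7.7 and 10.1 use only adverse events. Per-patient reporting would make a missing ADC value visible, and the shifts in step 4 are smaller than the sampling uncertainty. This stands, and it limits the severity.

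**Conclusion.** The point holds as a gap in the measurement rules. One radiologist traces and draws by hand, the plan does not require time point or reading order to be hidden, and the lesion set for follow-up ADC is undefined while low ADC helps decide what counts as a lesion. The reported mean volume change is therefore open to expectation. The mean ADC change may also omit lesions that have normalised.

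The size and net direction cannot be computed from the documents. The 14% to 49% range rests on assumed spheres and assumed edge shifts. The 0.17 to 0.42 SD shifts rest on normality and on an assumed loss of one or two of the best responders. It would go beyond the text to conclude that scans are in fact read with labels visible, or that responders are in fact dropped. Severity is low to moderate: the endpoint is secondary and descriptive, but it is the only measure for objective 2.1.6 and the repair is cheap.

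**What to change.** 1. **Masked re-measurement (Section 6.1.2.4).** After the last follow-up scan, the same radiologist re-measures both scans of every subject for the research endpoint, in random order, with dates and time-point labels hidden. This is 2 × 7 = 14 to 2 × 10 = 20 scans. The clinical baseline read for biopsy targeting stays as planned.
2. **ADC site (Section 6.1.2.6).** Define *confirmed* as confirmed at baseline, and measure ADC at that site on both scans even if the lesion is no longer visible. Locate the site on the follow-up scan by anatomical matching to the baseline MRI and biopsy map. This step must be written in, because Section 6.1.2.5 does not provide MRI-to-MRI transfer. The site can be marked on both scans after the masked volume tracing, so that marking does not influence the outlines.

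The cost is some reading and site-matching time, with no extra scan or reader. Masking will be imperfect, because treatment effect may be visible and the reader has already seen the baseline scans. It still removes the explicit label and the fixed reading order.

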6.1.2.5 MRI-US image fusion

Anatomic co-registration of biopsy samples and MRI findings are essential in this proposal. Transrectal ultrasound images will be fused with initial MRI performed prior to therapy using a specialized device (UroStation; Koelis, Grenoble, France). This technology allows 3-dimensional anatomic co-registration of volumetric transrectal ultrasound (TRUS) and MRI acquisitions. Once the TRUS and MRI volumes are co-registered, the urologist can use the real-time fusion dataset to perform routine sextant biopsies and also target biopsies directly to the suspicious areas on MRI. Furthermore, this system allows for saving a 3D map of the prostate with the biopsy tracts of the needle biopsies and data from pathologic analysis, once it becomes available, can be loaded into the system for further analysis. Because these 3D maps can be loaded into the biopsy US unit prior to performing the follow-up biopsy after treatment, we will use this capability to facilitate the anatomic coregistration of the initial pre-treatment biopsies and the repeat biopsy performed after treatment.²⁰

6.1.2.6 Evaluation of changes in tumor volume and tumor activity

Tumor volume will be assessed using a planimetric approach.²¹ On each MRI prostate section the outline of suspicious areas will be traced on the computer screen and the surface area will be calculated. After counting the number of separate foci and defining the most representative site of origin, tumor foci volume will be calculated by multiplying the sum of the suspicious surface areas by the slice thickness (usually 2-3 mm).

Tumor activity will be assessed using apparent diffusion coefficient (ADC) derived from diffusion-weighted imaging, which has been shown to correlate with Gleason score and percentage of tumor on core biopsy (as surrogates for tumor aggressiveness).^{22,23} ADC values will be derived by drawing a region of interest on the confirmed tumors, and expressed as mean values and histograms.

6.2 Safety/tolerability

Analyses will be performed for all subjects having received at least one dose of study drug. The study will use the CTCAE version 4.0 for reporting of non-hematologic adverse events (http://ctep.cancer.gov/reporting/ctc.html) and modified criteria for hematologic adverse events .

7.0 ADVERSE EVENTS

7.1 Experimental Therapy

For the most recent safety update, please refer to the current Investigator's Brochure or Study Agent Prescribing Information.

7.1.1 Contraindications: Enzalutamide is contraindicated in pregnancy.

7.1.2 Special Warnings and Precautions for Use: Seizure occurred in 0.9% of patients who received enzalutamide in a completed phase III trial. There is no clinical trial experience with enzalutamide in patients who have had a seizure, in patients with predisposing risk factors for

seizure, or in patients using concomitant medications that may lower the seizure threshold. Patients with a history of seizure or with predisposing risk factors for seizure are ineligible to participate in this study.

7.1.3 Interaction with other medications:

In vitro studies show that enzalutamide and/or metabolite M2 are potential inhibitors of CYP2C8 and CYP2C19 with lesser potential for inhibitory effects on CYP2B6 and CYP2C9. Enzalutamide is a moderate CYP2C9 and CYP2C19 inducer in humans. For this study, substrates of CYP2B6, CYP2C8, CYP2C9, and CYP2C19 that have a narrow therapeutic index (e.g., paclitaxel, phenytoin, warfarin, omeprazole) are prohibited during the period of enzalutamide administration.

In vitro studies show that enzalutamide is an inducer of CYP3A4. Induction of CYP3A occurs via activation of the nuclear pregnane X receptor (PXR), which is expected to result in co-induction of CYP2C. Co-administration of enzalutamide with CYP3A or CYP2C substrates may reduce oral bioavailability and/or accelerate elimination of these substrates. Enzalutamide is a strong CYP3A4 inducer in humans. For this study, narrow therapeutic index drugs that are metabolized by CYP3A4 (e.g., alfentanil, cyclosporine, dihydroergotamine, ergotamine, fentanyl, pimozide, quinidine, sirolimus and tacrolimus) are prohibited.

In vitro studies show that enzalutamide is metabolized by CYP2C8 and CYP3A4/5. Strong inhibitors or inducers of these enzymes may affect enzalutamide exposures. Coadministration of a strong CYP2C8 inhibitor (gemfibrozil) increased the composite area under the plasma concentration-time curve (AUC) of enzalutamide plus N-desmethyl enzalutamide in healthy volunteers. For this study, co-administration of enzalutamide and strong CYP2C8 inhibitors (e.g., gemfibrozil) is prohibited. Co-administration of a strong CYP3A4 inhibitor (itraconazole) increased the composite AUC of enzalutamide plus Ndesmethyl enzalutamide by 1.3 fold in healthy volunteers. For this study, coadministration of enzalutamide and strong inhibitors of CYP3A4/5 (e.g., clarithromycin, itraconazole, ketoconazole) are prohibited.

Use caution when co-administering strong inducers of CYP2C8 (e.g., rifampin) or CYP3A4/5 (e.g., carbamazepine, phenytoin, rifampin, St. John's wort) during enzalutamide treatment, as enzalutamide concentrations may decrease.

In vitro studies show that enzalutamide and metabolite M2 are potential inhibitors of the efflux transporter P-gp. Co-administration of enzalutamide with P-gp substrates may increase the plasma concentrations of the P-gp substrate. Use caution when co-administering sensitive P-gp substrates (e.g., colchicine, dabigatran etexilate, digoxin) during enzalutamide treatment.

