3.0 Subject ELIGIBILITY

Eligibility waivers are not permitted. Subjects must meet all of the inclusion and exclusion criteria to be registered to the study. Study treatment may not begin until a subject is registered.

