3.2 Exclusion Criteria

- 3.2.1 Prior treatment with the following agents known to have endocrine effects on prostate cancer: GnRH agonist, GnRH antagonist, anti-androgen (bicalutamide, nilutamide, flutamide), ketoconazole, diethylstilbestrol, estrogen, abiraterone acetate. Concurrent use of 5α -reductase inhibitors finasteride or dutasteride is permitted for patients who have been already receiving either of these treatments for at least 1 month at the time of study enrollment. Baseline PSA must have been obtained in such patients after at least 1 month on 5α -reductase treatment. Initiation of treatment with 5α -reductase inhibitors is not permitted within the first 12 months of study participation.
- 3.2.2 Concomitant treatment with agents thought to have endocrine effects on prostate cancer: PC-SPES, saw palmetto
- 3.2.3 Treatment with corticosteroids within 4 weeks prior to enrollment.
- 3.2.4 Treatment with androgens within 6 months prior to study enrollment.
- 3.2.5 Subjects may not be receiving any other investigational agents. Concurrent enrollment in another clinical investigational drug or device study is prohibited.
- 3.2.6 Prostate cancer metastases to the bones, viscera, or non-regional lymph nodes (lymph nodes other than pelvic lymph nodes within the radiation treatment field)
- 3.2.7 Serum PSA > 160 ng/dL
- 3.2.8 History of malignancy (other than non-melanoma skin cancer) within 5 years of enrollment
- 3.2.9 Patients with histologic evidence of small cell carcinoma of the prostate will not be eligible.
- 3.2.10 Treatment for malignancy with anticancer therapy, including cytotoxic agents, hormonal agents, or immunotherapy, within 5 years of enrollment
- 3.2.11 History of allergic reactions attributed to compounds of similar chemical or biologic composition to *enzalutamide* or other agents used in this study.
- 3.2.12 Uncontrolled intercurrent illness including, but not limited to, ongoing or active infection, symptomatic congestive heart failure (> NYHA class II hear failure), unstable angina pectoris, cardiac arrhythmia, chronic active hepatitis, acute hepatitis, uncontrolled diabetes mellitus, or psychiatric illness/social situations that would limit compliance with study requirements.
- 3.2.13 Patients with any of the following within 6 months of enrollment: deep vein thrombosis, pulmonary embolus, myocardial infarction, cerebrovascular accident, unexplained loss of consciousness.

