- 3.2.14 Patients with any history of seizure or seizure disorder.
- 3.2.15 Patients with medical conditions which, in the opinion of the investigators, would pose undue risk to the patient
- 3.2.16 Subjects unwilling to use contraceptives if they have sexual intercourse with a female partner of child-bearing potential while receiving treatment on this study.
- 3.2.17 Standard contraindications to MRI: For example, MRI non-compatile cardiac pacemakers, intracranial clips, foreign metal objects in the body and others as defined in the UT Southwestern Institutional MRI Safety Policy)
- 3.2.18 The following medications are prohibited during the study:
 - Substrates of CYP2B6, CYP2C8, CYP2C9, and CYP2C19 with a narrow therapeutic index, including paclitaxel, phenytoin, warfarin, omeprazole
 - Substrates of CYP3A4 with a narrow therapeutic index, including alfentanil, cyclosporine, dihydroergotamine, ergotamine, fentanyl, pimozide, quinidine, sirolimus, tacrolimus
 - Strong CYP2C8 inhibitors, including gemfibrozil
 - Strong CYP3A4/5 inhibitors, including clarithromycin, itraconazole, ketoconazole

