5.1.1 Informed Consent

5.1.2 Medical history

Complete medical and surgical history, history of infections

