11.4 Adherence to the Protocol

Except for an emergency situation in which proper care for the protection, safety, and well-being of the study subject requires alternative treatment, the study shall be conducted exactly as described in the approved protocol.

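### Section 7.1.2 bars men with predisposing risk factors for seizure, but the Section 3 criteria used for registration do not carry that exclusion

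*Combined protocol and SAP*

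**What the plan says.** Section 7.1.2 (Special Warnings and Precautions for Use) makes two groups ineligible: "Patients with a history of seizure or with predisposing risk factors for seizure are ineligible to participate in this study".

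Section 3.0 ties registration to the Section 3 list and allows no waivers: "Subjects must meet all of the inclusion and exclusion criteria to be registered to the study". The Registration Procedures in Section 11.2 have eligibility confirmed with the study coordinator before a man is registered.

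The criterion in that list that names seizure is 3.2.14: "Patients with any history of seizure or seizure disorder". Three others bear on seizure risk without naming it:

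- 3.2.13: "Patients with any of the following within 6 months of enrollment: deep vein thrombosis, pulmonary embolus, myocardial infarction, cerebrovascular accident, unexplained loss of consciousness".
- 3.2.15: "Patients with medical conditions which, in the opinion of the investigators, would pose undue risk to the patient".
- 3.2.6 excludes metastases to bone, viscera or lymph nodes outside the pelvis.

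Section 11.4 says that, emergencies apart, "the study shall be conducted exactly as described in the approved protocol".

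**The concern.** One part of the protocol states a mandatory exclusion, and the list applied at registration does not contain it. This is an internal inconsistency about who may enter the trial. A coordinator who works through Section 3 item by item has no prompt to apply the second half of the 7.1.2 rule, which sits in a chapter on adverse events.

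The subject is not minor. Safety and tolerability are the primary endpoint. Section 7.7 ranks seizure first among the safety concerns with enzalutamide, and Section 7.1.2 says that no clinical trial has tested the drug in men with predisposing risk factors. Section 4.2 stops enzalutamide and removes the subject after a seizure, so it cannot prevent the first one. Screening is the preventive step, and it should not depend on whether someone recalls a sentence elsewhere or chooses to invoke 3.2.15.

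**Working it through.** No arithmetic applies, because the point depends on no error rate, effect size or sample size. The check sets each relevant criterion against the second half of the 7.1.2 rule.

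| Criterion | What it removes | Does it carry the risk-factor exclusion? |
|---|---|---|
| 3.2.14 | Past seizure or seizure disorder | No; it covers the first half of the rule |
| 3.2.13 | Stroke or unexplained loss of consciousness, among vascular events, within 6 months | In part; time-limited and not labelled a seizure criterion |
| 3.2.6 | Bone, visceral and non-regional nodal metastases | In part; largely removes metastatic disease outside the pelvis, though the brain is not named |
| 3.2.15 | Conditions the investigator thinks pose undue risk | By discretion, whereas 7.1.2 is mandatory |

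No item in 3.1 or 3.2 names predisposing risk factors for seizure, and the text available for review does not define the term.

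Two candidates show what passes through. Each rests on a stated assumption about what counts as a risk factor.

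**Candidate A** has documented brain atrophy with microvascular disease and no past seizure, stroke, loss of consciousness or metastasis. Section 1.2.2 mentions such findings when it describes the five phase 3 patients with seizures: two had brain metastases, one had received a lidocaine overdose, one had recently started haloperidol against a background of heavy drinking and brain atrophy, and one had cortical atrophy with microvascular disease. Suppose the sponsor counts these as predisposing factors. Then 7.1.2 bars him, while 3.2.6, 3.2.13 and 3.2.14 do not. He is kept out under Section 3 only if the investigator uses 3.2.15.

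**Candidate B** had a stroke 8 months before enrollment. Suppose a past stroke counts. Then 7.1.2 bars him, but he is 8 − 6 = 2 months outside the 3.2.13 window, and 3.2.14 does not apply.

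In each case the man passes every named Section 3 criterion, and registering him would breach 7.1.2, which Section 11.4 makes binding. The screening history in Section 5.1.2 is broad ("Complete medical and surgical history, history of infections") and might bring such a condition to light. But without a criterion or a definition to test it against, two coordinators could decide the same case differently.

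**The case against.** The strongest reply is that the two rules can be obeyed together. Section 3.0 makes its criteria necessary for registration and does not say that they suffice. Section 7.1.2 adds a restriction, Section 11.4 binds it, and 3.2.15 offers a route for applying it. That stands. A reader might infer that men with seizure risk factors are unprotected, or that the protocol gives instructions that cannot both be followed. The documents support neither reading. What remains is that the list used at registration is looser than a mandatory rule stated elsewhere.

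A second reply is that other criteria already remove much of the risk. That stands in part. It would be wrong to say that Section 3.2 deals with seizure risk through seizure history alone, given 3.2.13 and 3.2.6. Criteria 3.2.8 (other malignancy within 5 years) and 3.2.12 (uncontrolled intercurrent illness) may remove a few more. None of them reaches candidate A.

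A third is that the 6-month window for stroke may be a deliberate choice. That is a fair reading and makes candidate B the weaker example. It is also a reason for the text to say how older events are treated.

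A fourth is that the complete history, the eligibility review in 5.1.4 and the medication review in 5.1.5 would catch such men. They may supply the facts, but they do not supply the rule.

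Two further inferences should be resisted. The overall phase 3 seizure rate in Section 4.2 does not measure the effect of this mismatch, because it is not the rate in the men concerned. And although 7.1.2 also notes a lack of experience "or in patients using concomitant medications that may lower the seizure threshold", its ineligibility sentence does not name those users, so their handling is a separate matter.

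**Conclusion.** The inconsistency is real and should be fixed. Section 7.1.2 excludes men with predisposing risk factors for seizure; the Section 3 criteria do not, beyond partial overlap and investigator discretion. A man barred by the one can be registered under the other.

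The size is limited. No statistical figure in the plan changes. The documents give neither the share of candidates with such factors nor their seizure rate, so the effect cannot be computed.

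The conclusion rests on the current text and on three qualifications. The two candidates depend on what the sponsor counts as a risk factor. The absence of a definition is a statement about the text available for review, in which a part between Sections 7.1.3 and 7.2 is missing. And the documents do not say whether 7.1.2 or 3.2.14 reflects the sponsor's intent.

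**What to change.** Extend 3.2.14 so that, besides past seizure and seizure disorder, it excludes documented predisposing risk factors for seizure. Follow it with a short list chosen by the sponsor, for example conditions of the kind Section 1.2.2 describes in the seizure cases, such as brain atrophy or microvascular disease. State how a stroke or loss of consciousness older than 6 months is treated, so that 3.2.13 and 3.2.14 agree. Have 7.1.2 refer to 3.2.14 in place of stating its own rule.

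If the sponsor did not intend the broader exclusion, align 7.1.2 to 3.2.14 and 3.2.15. The stricter rule is the safer default, given the stated lack of trial experience in such men.

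The cost is one reworded criterion, one sentence on older events and one cross-reference. Because the list is confined to documented conditions, no new screening test is needed; the Time and Events Table schedules no brain imaging. A few candidates may be screened out, but 7.1.2 already bars them.
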